## 11.2 Peripheral Blood Biomarkers Predicting Chemotherapy Tolerability

Peripheral blood biomarkers (IL-6, CRP, D-dimer) analysis will be performed on samples collected at baseline after 3 cycles, and at end of study when patient receives geriatric assessment. At each of the required time points, two tubes of venous blood (10 mL) will be collected into a K2EDTA tube (purple top) and will be transported on ice to [name] laboratory in the 1st floor of the Shapiro Clinical Research Bldg., Room 1042., one for peripheral blood biomarkers and one for ctDNA. A medical log will be kept in each laboratory, to be filled out by the deliverer of the samples, and signed off by a member of [name] lab. A receipt will be made and stored in the patient's chart for future record keeping. This will ensure safety and proper identification of the sample. Plasma will be separated from whole blood by centrifugation at 1,500 x g for 10 minutes at 4° C and transferred to appropriately-labeled polypropylene tubes and frozen at  $\leq$  -20°C. Specimens will be batched at each participating site and stored in freezers at each site. At City of Hope, the specimens will be stored in a freezer accessible only to members of [name] laboratory. Each tube will be labeled with the study number, patient registration number, time point, and the date and time the sample was drawn.

Peripheral blood biomarkers (IL-6, CRP, D-dimer) analysis will be performed on samples collected at baseline after 3 cycles, and at end of study when patient receives geriatric assessment. Methods for measuring the three biomarkers are well established with enzyme-linked immunosorbent assays. For plasma biomarker measurement, 7.5 ml peripheral blood is

collected prior to initiation of chemotherapy. Plasma is stored at -80 °C until assays are run. Quantitative IL-6 and CRP levels will be obtained using NOVEX® immunoassay (Invitrogen) and D-dimer levels will be measured with Nanopia® D-dimer (Sekisui).

Circulating DNA fragments carrying tumor-specific sequence alterations (ctDNA) are found in the cell-free fraction of blood, representing a variable and generally small fraction of the total circulating DNA. Advances in sequencing technologies have enabled the rapid identification of somatic genomic alterations in individual tumors, and these can be used to design personalized assays for the monitoring of ctDNA. Studies have shown the feasibility of using ct DNA to monitor tumor dynamics in a limited number of patients with various solid cancers, but few cases of breast cancer have been analyzed [65].

### **11.3 Specimen Labeling and Shipping**

Tubes containing plasma samples must be clearly labeled, preferably with a printed label containing the following information:

- 1) An anonymized number that clearly indicates the site at which the sample was accrued and processed. For example, samples from City of Hope could be labeled COH001, COH002 etc. The [name] lab wishes to remain blinded throughout the duration of this study. Therefore, it is the responsibility of each site to maintain a record of the anonymized sample numbers sent to the [name] Lab and the patient ID#'s linked to them.
- 2) Date and time when the patient's blood draw was performed.
- 3) The IRB Protocol # associated with the collection of the sample.

Every 4 months, frozen plasma will be shipped from participating sites to [name] laboratory at City of Hope. The specimens will be shipped via FedEx Priority Overnight® on dry ice to ensure the specimens remain frozen during transportation.

[name]  
 Clinical Immunobiology Correlative Studies Laboratory (CICSL)  
 Shapiro Building Room 10-12-1044  
 City of Hope Comprehensive Cancer Center  
 [name]  
 Duarte, CA 91010

### **11.4 Bacteriomic Profiling**

#### **11.4.1 16S Gut Microbiome rRNA analysis**

Fecal samples are relatively easy to collect and non-invasive. They provide an indication of the gut microbiome which may be an indicator of general health, impact drug availability, and indicate the presence of communities associated with inflammation, digestive inefficiencies, and pathogens. Monitoring the gut microbiome may allow us to predict the risk of possible side effects of targeted therapy (colitis and decreased appetite) and therapeutic efficacy

The exploratory objective to monitor the gut microbiota at baseline, on treatment and end of treatment using fecal samples. The differences in gut microbiota within and between fecal samples will be compared using alpha and beta diversity metrics based on 16S rRNA sequencing.

#### **11.4.2 Stool Specimen Collection**

Fecal material will be collected in a Zymo Research DNA/RNA Shield Fecal Collection Tube by patients as instructed. A standard operating procedure (SOP) has been generated for stool collection, as outlined in Appendix O. Stool collection kit contents are listed in Appendix Q. A copy of this SOP will be provided to the patient and their understanding of the SOP will be documented by the PI.

Samples will be collected pre-treatment (within 7 days prior to start of Neratinib), C1Day 15 (+/- 3 days), C2Day1 (+/-3 days), C2Day15 (+/-3 days), C3Day1 (+/-3 days). Patient will bring samples on the scheduled study visits.

All samples will be collected by participants at home or during study visit. Study team will collect the samples and transport to Biospecimen Coordinator in COH Biorepository.

## 12.0 Experimental Design Schema

	Pre-Study (up to 28 days prior to enrolling) i	Cycle 1 Day 1 (28 day cycle)	Cycle 1 Day 8 (± 1 day)	Cycle 1 Day 15 (± 1 day)	Cycle 2 Day 1 (± 3 days)	Cycle 2 Day 15 (± 3 days)	Cycle 3 Day 1 (± 3 days)	Cycle 4 Day 1 (± 3 days)	Cycle 5 Day 1 (± 3 days)	Cycle 6 Day 1 (± 3 days)	Every Cycle Thereafter (± 3 days)	Every 3 cycles (± 7 days)	Off Treatment h
Neratinib (day 1-7 of each wk) a,b		X	X	X	X	X	X	X	X	X	X		
Demographics	X												
Medical history	X												
Concurrent meds (± 1 wk)	X	X			X		X	X	X	X	X		X
Physical exam (± 1 wk)	X	X			X		X	X	X	X	X		X
Vital signs (± 1 wk)	X	X			X		X	X	X	X	X		X
Height	X												
Weight (± 1 wk)	X	X	X	X	X	X	X	X	X	X	X		X
Performance Status (± 1 wk)	X	X			X		X	X	X	X	X		X
CBC w/diff, plts (± 1 wk)	X	X			X		X	X	X	X	X		X
Complete Metabolic Panel c (± 1 wk)	X	X	X	X	X	X	X	X	X	X	X		X
Diarrhea Checklist		X l											
Nurse brief toxicity evaluation		X	X	X	X	X	X						
EKG	X												
Pharmacokinetic samples j				X			X	X					
Adherence evaluation (pill count, diaries) (± 1 wk)		X	X	X	X	X	X	X	X	X	X		
Adverse event evaluation (± 1 wk)		X	X	X	X	X	X	X	X	X	X		X
Tumor measurements using CT or PET-CT (± 1 wk)	X d							X				X e	X f
LVEF Assessment	X d							X e				X e	X f
Geriatric Assessment Survey(±1 wk) k	X							X					X g
Peripheral Blood Correlatives k	X							X					X
Bacteriomic profiling	X m			X	X	X	X						

---

- a: Dose as assigned; neratinib 240mg orally daily; Doses held due to toxicity will not be made up.
- b: If baseline laboratory tests are done within 14 days of start of treatment, these labs do not need to be repeated prior to Day 1.
- c: Albumin, alkaline phosphatase, total bilirubin, bicarbonate, BUN, calcium, chloride, creatinine, glucose, potassium, total protein, SGOT[AST], SGPT[ALT], sodium.
- d: Baseline assessment may be done up to 30 days prior to study enrollment.
- e: Tumor measurements and LVEF assessment are repeated every 3 months  $\pm$  1 wk until patient comes off study. Documentation (radiologic or clinical) must be provided for patients removed from study for progressive disease.
- f: Off-study radiologic evaluation will only be done if clinically indicated.
- g: Geriatric assessment will be performed at baseline prior to study, after 3 cycles ( $\pm$ 7 days) and at end of study ( $\pm$ 7 days). Geriatric assessment will be repeated off study ONLY if it had not been administered within the previous month. If patient's native language was not covered by the current language forms, Geriatric assessment form can be omitted with clear documentation.
- h: Patients will be followed for 30 days following discontinuation of therapy in order to capture toxicity attributable to therapy.
- i. Chart review data must be within 28 days to determine if patient meets study criteria. Once patient meets study criteria, then all criteria must be within window specified in protocol from Day 1 as indicated in column one in the schema above.
- j: Pharmacokinetics samples will be collected at the following time points: Cycle 1 Day 15 pre-dose ( $\pm$  20 minutes) and 6 hours post-dose ( $\pm$  60 minutes); pre-dose ( $\pm$  20 minutes) on Cycle 3 Day 1 and Cycle 4 Day 1. All pre-dose samples should be collected within 30 minutes before the daily dose in 10 ml purple-top tube.
- k: Peripheral blood correlates for inflammatory marker measurement (IL-6, CRP and D-dimer) and ctDNA will be collected in 10 ml purple-top tube at baseline, after 3 cycles (Cycle 4 Day 1  $\pm$  7days), and at end of study ( $\pm$ 7days) when patient receives geriatric assessment.
- L: An "Optimal Management of Diarrhea Checklist" will be reviewed and signed by study investigator or study nurse on Cycle 1 Day1. The study team will call patients at 1day, 2 days and 3 days after first dose of neratinib to assess tolerance.
- m. Stool samples must be collected within 7 days prior to start of neratinib, C1Day 15 (+/-3 days), C2Day1 (+/-3 days), C2Day15 (+/-3 days), C3Day1 (+/-3 days).

## **13.0 Endpoint Evaluation Criteria/Measurement of Effect**

---

### **13.1 Response Criteria**

For the purposes of this study, patients should be reevaluated for response every 12 weeks. Response and progression will be evaluated in this study using the new updated international criteria proposed by the Response Evaluation Criteria in Solid Tumors (RECIST) Committee version 1.1. Per the RECIST criteria, as disease response is not the primary endpoint of this trial, confirmatory scans following documentation of progression or response will not be required. Rather, progression/response will be determined based on results of the single scan.

### **Definitions**

Evaluable for toxicity: All patients will be evaluable for toxicity from the time of their first treatment with Neratinib.

Evaluable for objective response: Only those patients who have measurable disease present at baseline, have received at least one cycle of therapy, and have had their disease re-evaluated will be considered evaluable for response. These patients will have their response classified according to the definitions stated below. (Note: Patients who exhibit objective disease progression prior to the end of cycle 1 will also be considered evaluable.)

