#### *1.4.6.1 Neratinib Single-agent Activity in Patients with HER2+ Breast Cancer*

Early clinical data have demonstrated the activity of neratinib in patients who have already failed other small molecule or antibody-based HER2 targeted therapies. In the single-agent, first-in-human phase I study of neratinib in solid tumor, a 32% objective response rate (ORR) was observed among patients with trastuzumab refractory HER2+ disease [5]. Specifically, 8 of 25 patients had partial response (PR). Among the responders, two PRs occurred at neratinib doses of 120 or 180 mg per day, which was below the recommended monotherapy dose. All of these responders had prior trastuzumab therapy, notably six patients had received at least four trastuzumab-based therapies. Additionally, all had received prior anthracycline and gemcitabine, and the majority (7/8) had received prior taxane therapy. Six patients had also received prior capecitabine therapy.

An open-label, multicenter, Phase 2 study evaluated the efficacy and safety of neratinib 240 mg daily, in patients with and without prior trastuzumab treatment, who had advanced HER2+ breast cancer. The primary end point, the 16-week PFS rates, was 59% and 78% in prior trastuzumab-treated patients and trastuzumab-naïve cohorts, respectively [4]. The ORR was 24% and 56%, respectively, and the median PFS times were 22.3 and 39.6 weeks, respectively. Mean steady-state trough concentrations for the 240 mg daily dose exceeded concentrations needed to inhibit autophosphorylation of HER2 in preclinical models [18].

The most common adverse events (AE) were diarrhea, nausea, vomiting, and fatigue. Diarrhea was the most frequent Grade 3 to 4 AE, occurring in 30% of patients with prior trastuzumab treatment and in 13% of trastuzumab-naïve patients, which resulted in dose reductions of 29% and 4% of patients, respectively. However, treatment discontinuation (TD) occurred in only one patient due to diarrhea (Grade 2). No neratinib-related Grade 3 or 4 cardiotoxicity was reported. Additional information regarding previous clinical studies of neratinib for treatment of HER2+ breast cancer is provided in the current Investigator's Brochure.

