## 13.9 Clinical Benefit Rate

The CBR is defined as the proportion of patients who achieved overall tumor response (CR or PR) or SD for at least 24 weeks. Stable disease is measured from enrollment until the criteria for disease progression or response are met, per RECIST v1.1

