### 15.3 Data Analysis

Tables will be created to summarize the toxicities and side effects by organ system, attribution and severity for all participants that receive at least one dose of neratinib.

Rates and associated 95% exact Clopper and Pearson binomial confidence limits will be estimated for 1) grade 2 or higher toxicities attributed to neratinib, 2) all grade GI toxicities (diarrhea, nausea and vomiting), 3) dose reductions, holds and hospitalizations, and 4) the objective response (CR+PR) and clinical benefit (CR+PR+SD) and 5) 16 week progression free survival(PFS). EFS, PFS and OS will be estimated using the product limit method of Kaplan and Meier. Descriptive statistics will be provided for drug adherence and participant demographics. Serum samples from this study will be integrated into a population PK analysis dataset to explore the effects of age on PK parameters (clearance and volume of distribution) and exposure-response relationships on efficacy and safety of neratinib. Generalized linear models and graphical methods will be used to explore factors as identified by a cancer-specific geriatric assessment and serum biomarkers that may be predictive of toxicity dose reductions, dose holds or hospitalizations. We will use generalized linear models to determine if any of these factors independently predict toxicity, response, and/or pharmacokinetic parameters of interest.

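### Section 15.3 names no ORR denominator, and the only response-evaluable set (13.1) omits treated patients never re-assessed, so ORR is likely, though not certain, to read somewhat high

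*Combined protocol and SAP*

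**What the plan says.** Section 15.3 lists the rates that will carry Clopper-Pearson limits. Item 4 reads "4) the objective response (CR+PR) and clinical benefit (CR+PR+SD" and continues without naming a population. The one population named in 15.3, "for all participants that receive at least one dose of neratinib", belongs to the sentence on toxicity tables. The statistical paragraph of the synopsis has the same gap.

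The Definitions under 13.1 set the response population as follows: "Only those patients who have measurable disease present at baseline, have received at least one cycle of therapy, and have had their disease re-evaluated". One exception follows: "Patients who exhibit objective disease progression prior to the end of cycle 1 will also be considered evaluable".

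On timing, 13.1 says that "patients should be reevaluated for response every 12 weeks". Footnote f of the schedule in 12.0 adds: "Off-study radiologic evaluation will only be done if clinically indicated".

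Clinical benefit is worded differently in 13.9: "The CBR is defined as the proportion of patients who achieved overall tumor response (CR or PR) or SD for at least 24 weeks". No evaluability condition is attached to it. No section says that a treated patient without a post-baseline assessment counts as a non-responder.

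**The concern.** The secondary objective is the response rate in adults 60 and older who are given neratinib. A denominator that requires a completed cycle and a re-assessment is selected partly by who tolerates the first weeks of drug, and tolerability is the trial's main question. A patient never re-assessed cannot be a recorded responder, so leaving that patient out can only raise ORR compared with counting a non-response.

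There is a real route to this loss. Section 7.6.1.1 places the onset of diarrhea in the first few weeks, whereas the first scheduled scan is at 12 weeks. Table 8 includes a recommendation to discontinue for the more serious diarrhea events. Section 8.5 withdraws patients from active treatment after non-cardiac holds of more than 28 days. Section 7.5 ends active follow-up at removal from study, and off-study imaging is not routine. A patient who stops in the first 11 weeks may therefore never be re-assessed.

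**Working it through.** **Step 1. The plan's own precision figures.** Section 15.1 gives limits of .09 and .36 for 8/40, a widest half-width of 0.16, and an 87% chance of seeing a toxicity whose true rate is 0.05. With Clopper-Pearson limits (lower = 2.5% quantile of Beta(x, n−x+1), upper = 97.5% quantile of Beta(x+1, n−x)), 8/40 gives 0.0905 to 0.3565. The largest half-width over x = 0 to 40 is 0.162, and 1 − 0.95^40 = 0.871. All three reproduce. They concern toxicity in all 40 patients and do not settle the ORR denominator.

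**Step 2. Who is in the 13.1 set.** For treated patients with measurable disease at baseline:

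| Course | In the set? | Effect on ORR of leaving out |
|---|---|---|
| One cycle or more, re-assessed | Yes | none |
| Objective progression before end of cycle 1 | Yes | none |
| Stops for toxicity, never re-assessed | No | up |
| Dies before any re-assessment | No | up |
| Deteriorates clinically, never re-assessed | No | up |
| Stops in cycle 1 without progression, re-assessed later | No | up if non-responder, down if responder |

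Dose holds and reductions alone remove no one, because 8.0 keeps tumor assessments on schedule. Section 13.3 allows superficial lesions to be measured clinically, so being unassessed is narrower than being unscanned.

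**Step 3. Direction.** Let r of n measurable patients respond. Leave out j patients with a recorded response and k without one. ORR rises if (r − j)/(n − j − k) > r/n, which rearranges to j/(j + k) < r/n. The shift is upward as long as the share of responders among those left out is below the ORR itself. In the three never-assessed rows j = 0, so those rows can only push upward.

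**Step 4. Size, by illustration only.** The documents give no count of patients with measurable disease and no rate of loss before first assessment. Assumed inputs:
- n = 30 of the 40 have measurable disease (non-measurable disease is eligible under 5.1).
- r = 7, since 24% of 30 is 7.2. The 24% is the ORR in trastuzumab-pretreated patients in 1.4.6.1.

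Results, with exact 95% limits:
- Nobody left out: 7/30 = 23.3% (9.9 to 42.3).
- One unassessed patient left out: 7/29 = 24.1% (10.3 to 43.5), +0.8 points.
- Two left out: 7/28 = 25.0% (10.7 to 44.9), +1.7 points.
- Reverse case, one cycle-1 stopper who later responds left out: 6/29 = 20.7% (8.0 to 39.7), −2.6 points.

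Varying n, with two unassessed patients left out:
- 6/25 = 24.0% becomes 6/23 = 26.1% (+2.1 points).
- 8/35 = 22.9% becomes 8/33 = 24.2% (+1.4 points).
- 10/40 = 25.0% becomes 10/38 = 26.3% (+1.3 points).

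Every shifted estimate lies well inside the interval for the unshifted one.

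**The case against.** The strongest reply is that 13.1 defines the evaluable set in advance, in the section on endpoint evaluation. If it is the denominator, then the denominator is specified and the analyst has little freedom. If it is not, nothing shows that ORR will be overstated. The first half stands in part: a reader might infer that the denominator is open to choice after the data are seen, and a prospective definition in 13.1 makes that reading weak. What remains is that 15.3 does not refer to 13.1, and that following 13.1 as written drops patients whose outcome is known not to be a recorded response.

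The lost group is also probably small. Section 1.4.6.1 reports that in the single-agent phase 2 study "treatment discontinuation (TD) occurred in only one patient due to diarrhea (Grade 2". Section 5.1 requires a life expectancy above 12 weeks, 7.4 asks for imaging confirmation of progression, and the note to Table 15 asks for effort to document progression after clinical deterioration. This stands, with one reservation: 1.7 says that only 38 of 291 patients in six neratinib trials were 65 or older, so the reassurance may not carry over fully.

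A reader might infer a larger shift from the 6.1% diarrhea discontinuation in 1.4.5.4 or from the 12-16% grade 3-4 diarrhea in 1.4.5.5. Neither measures never-assessed patients. The first comes from a pooled safety population of 4242 with no 12-week limit, and a patient who discontinues may still be re-assessed. The second is an incidence, and Table 8 provides for hold and reduction in shorter grade 3 events.

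Finally, a reader might call it an error that ORR and CBR could have different denominators. It is not one in itself. Non-measurable disease is eligible and can be classified under 13.5, so a wider CBR set can be legitimate. Only the absence of a statement is a gap.

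**Conclusion.** The point holds in a limited form. Section 15.3 names no ORR denominator. The one response population defined leaves out treated patients with measurable disease who are never re-assessed, and no rule counts them as non-responders. If that set is used, ORR is likely to be somewhat high.

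This rests on two things: the inference that the 13.1 set is the denominator, and the expectation that most patients left out would have no recorded response. The stronger claim, that ORR is bound to be overstated, is not supported, because the one-cycle condition can also remove a responder.

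The size cannot be derived from the documents. In the illustration it is about 1 to 2 points for one or two patients, against an interval roughly 32 points wide (42.3 − 9.9). ORR is a secondary endpoint with no threshold attached. Early deaths still count in PFS and OS under 13.7 and 13.8. The primary toxicity rate, the interim review and the diarrhea boundary are untouched. It is worth correcting because the correction is cheap.

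**What to change.** In 13.1 and 15.3:
- Define the ORR denominator as all patients with measurable disease at baseline who took any neratinib.
- Count those without a post-baseline disease assessment as non-responders.
- Classify patients who stop in cycle 1 by the response recorded before any new anticancer therapy. The cut-off is needed because 13.7 censors PFS at new therapy, while best overall response in 13.5.1 has no such limit. Without it, a response to a later drug could be credited to neratinib.
- Report the number unassessed, with reasons.
- Give the ORR in the present 13.1 set as supportive.
- State the CBR denominator alongside. It may be wider than the ORR denominator, since patients with non-measurable disease are eligible.

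The cost is one definition in 13.1 and one or two lines in 15.3, matched in the synopsis, using data already collected. The reported ORR may be slightly lower.

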### **13.2 Disease Parameters**

Measurable disease: Measurable lesions are defined as those that can be accurately measured in at least one dimension (longest diameter to be recorded) as >10mm with conventional techniques (CT, MRI, or caliper measurement) and as >20mm by chest X-ray (if clearly defined and surrounded by aerated lung.) Lymph nodes greater than 10mm on short axis are considered measureable as well. All tumor measurements must be recorded in millimeters (or decimal fractions of centimeters).

Non-measurable disease: All other lesions (or sites of disease), including small lesions (longest diameter <20 mm by chest X-ray or <10 mm using CT, MRI or caliper measurement), are considered non-measurable disease. Organomegaly, leptomeningeal disease, ascites, pleural/pericardial effusions, lymphangitis cutis/pulmonis, inflammatory breast disease, and abdominal masses (not followed by CT or MRI) are all non-measurable.

Target lesions: All measurable lesions up to a maximum of two lesions per organ and five lesions in total, representative of all involved organs, should be identified as target lesions and recorded and measured at baseline. Lymph nodes less than 15mm in the short axis cannot be used as target lesions. Target lesions should be selected on the basis of their size (lesions with the longest diameter) and their suitability for accurate repeated measurements (either by imaging techniques or clinically). A sum of the longest diameter

---

(LD) for all target lesions will be calculated and reported as the baseline sum LD. The baseline sum LD will be used as reference by which to characterize the objective tumor response.

Non-target lesions: All other lesions (or sites of disease) including any measurable lesions over and above the 10 target lesions should be identified as non-target lesions and should also be recorded at baseline. Measurements of these lesions are not required, but the presence or absence of each should be noted throughout follow-up.

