## 13.4 Response Criteria

### 13.4.1 Evaluation of Target Lesions

Complete Response (CR): Disappearance of all target lesions. Lymph node CR is when the lymph node has decreased to less than 10mm in the short axis.

Partial Response (PR): At least a 30% decrease in the sum of the longest diameter (LD) of target lesions, taking as reference the baseline sum LD.

Progressive Disease (PD): At least a 20% increase in the sum of the LD of target lesions, taking as reference the smallest sum LD recorded since the treatment started (including the baseline scan if that is the smallest), and at least a 5mm increase or the appearance of new lesions.

Stable Disease (SD): Neither sufficient shrinkage to qualify for PR nor sufficient increase to qualify for PD, taking as reference the smallest sum LD since the treatment started.

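### The response rules disagree on lymph nodes: a patient can be response-evaluable with no target lesion, and a mainly nodal target set can meet both CR and SD

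*Combined protocol and SAP*

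**What the plan says.** The relevant rules are all in Section 13 of the combined protocol and SAP.

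- **Who is evaluable for response** (Definitions, under 13.1): "Only those patients who have measurable disease present at baseline, have received at least one cycle of therapy, and have had their disease re-evaluated". A target lesion is not required. The text adds that these patients are classified by the definitions that follow it.
- **Measurable nodes** (13.2): "Lymph nodes greater than 10mm on short axis are considered measureable as well".
- **Target lesions** (13.2): "All measurable lesions up to a maximum of two lesions per organ and five lesions in total, representative of all involved organs" are to be targets, but "Lymph nodes less than 15mm in the short axis cannot be used as target lesions". The baseline sum adds the longest diameter (LD) of every target lesion, with no exception for nodes.
- **Non-target lesions** (13.2): all remaining lesions, "including any measurable lesions over and above the 10 target lesions".
- **Target response** (13.4.1): "Lymph node CR is when the lymph node has decreased to less than 10mm in the short axis". PR needs a fall of at least 30% in the LD sum. SD is whatever is neither PR nor PD on that sum.
- **Non-target response** (13.5): CR requires every non-target lesion to disappear and tumor markers to normalize. Any persisting lesion is an incomplete response, labeled SD. No node size is given.
- **Overall response** (Table 15): every row starts from a target-lesion status. The rows that accept any target status all end in PD.

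**The concern.** Two steps in the derivation of response lack a unique answer.

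First, a node can be large enough to put the patient in the response set but too small to supply the measurement that response is judged by. Second, a node qualifies and resolves on one axis but is summed on another, so the CR test and the SD test can both be met at the same scan. Section 13.1 waives confirmatory scans, so that one assessment decides the category.

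The objective response rate, the clinical benefit rate and, through progression, PFS depend on these rules. Section 13.7 says PFS is derived by program from adjudicated progression, and a program needs one rule per case. If the rules stay open, two analysts can follow the protocol and report different response counts from the same scans.

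**Working it through.** No sample-size or precision figure in Section 15 depends on these rules, so there is no stated figure to reproduce. The check applies the rules literally. Lesion sizes below are illustrations, written as short axis x LD.

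**1. Evaluable without a target lesion.** Let s be the short axis of a node.
- Measurable: s > 10 mm. Eligible as target: s ≥ 15 mm. The gap is 10 < s < 15 mm.
- Take a patient whose only measurable lesion is a 12 mm node. 12 > 10, so the patient has measurable disease and, once treated for a cycle and re-evaluated, is evaluable. 12 < 15, so there is no target lesion.
- The baseline LD sum has no terms, so the percentage change is undefined and neither the 30% nor the 20% test can be computed.
- Under 13.5, non-target CR is available by disappearance. If the node shrinks from 12 to 8 mm it has not disappeared, so it is an incomplete response, although 8 mm would satisfy the node CR size in 13.4.1.
- Table 15 cannot carry a non-target CR or SD to an overall CR or SD without a target status. Only its PD rows can apply.

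**2. CR and SD together.** Consider a target set of one node.

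| Baseline | Follow-up | Short axis < 10 mm? | LD fall | Categories met |
|---|---|---|---|---|
| 16 x 24 | 9 x 20 | yes | (24 − 20)/24 = 16.7% | CR and SD |
| 15 x 22 | 9 x 17 | yes | (22 − 17)/22 = 22.7% | CR and SD |
| 18 x 25 | 9 x 17 | yes | (25 − 17)/25 = 32.0% | CR and PR |

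The overlap occurs when the short axis falls below 10 mm while LD falls by less than 30%. The third row shows that it is not universal. A CR/PR overlap does not change ORR, since both count as response.

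**3. How far it extends.** Target CR requires every target lesion to qualify. Add a 20 mm non-nodal target that disappears to the first row: the sum goes from 24 + 20 = 44 to 20 + 0 = 20, a fall of 24/44 = 54.5%. The SD test is no longer met. The overlap therefore needs a wholly or mainly nodal target set.

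**4. Five versus ten.** The target definition stops at five. The non-target definition covers all other lesions, and the clause with the figure ten is only an inclusion. Lesions six to ten are non-target either way.

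**5. Size.** One patient moved between response and non-response changes ORR by 1/n.
- n = 40 (everyone evaluable): 10/40 = 25.0% (exact 95% CI 12.7 to 41.2) against 11/40 = 27.5% (14.6 to 43.9), a shift of 2.5 points.
- n = 20 (assumed, since Section 5.1 admits non-measurable disease): 1/20 = 5 points.
- Keeping one target-less patient as a non-responder rather than excluding that patient has a smaller effect: with assumed counts, 7/29 = 24.1% against 7/30 = 23.3%, or 0.8 points.

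**The case against.** The best defense has four parts.

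- **The cited standard governs.** Section 13.1 names RECIST 1.1. This has some force, but the Definitions text sends the classification to the protocol's own definitions, and those are what conflict. A general citation does not tell a programmer which local sentence to ignore.
- **CR naturally outranks SD.** The node CR rule is specific and SD is residual, so most readers would choose CR. That is sensible, but nothing states it for a single assessment; Section 13.5.1 ranks responses over time. What remains is an unstated order of precedence, not a forced misclassification.
- **Patients with only small nodes can still respond.** A reader might infer from the missing sum that they cannot. The documents do not support that, because 13.5 defines a non-target CR by disappearance. The defect is narrower: PR cannot be computed, and Table 15 has no path from that non-target CR to an overall CR.
- **The figure ten changes nothing.** A reader might infer that lesions six to ten are unclassified. They are not, because the non-target definition already takes all other lesions. This part of the defense stands; the number is an inconsistency with little practical effect.

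It is also fair to say that ORR is a single-arm descriptive estimate with wide limits, and that the documents do not say how often either nodal case will occur.

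**Conclusion.** The point holds as an internal inconsistency with limited consequences. Read literally, Sections 13.1 to 13.5 allow an evaluable patient with no target sum and no Table 15 row for CR, PR or SD. They also allow a wholly or mainly nodal target set to satisfy CR and SD at one scan with no stated precedence.

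Only ORR, CBR and PFS are touched. For CBR, if the 24-week minimum in 13.9 applies to SD alone, a switch between CR and SD matters only when the SD is shorter than that. The primary toxicity endpoint, the sample size of 40 and the diarrhea boundary are unaffected.

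The shift of 2.5 to 5 points of ORR per reclassified patient assumes 20 to 40 evaluable patients. The total effect cannot be estimated, because the documents do not give the number of affected patients. The worked node sizes show that the conflict can occur, not how often.

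**What to change.** Make these edits in Section 13, checked against the cited criteria, before response is derived.

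1. **Node cut-off.** Use one short-axis limit, the existing 15 mm target limit, for both measurable and target nodes in 13.2. Alternatively, require at least one target lesion in the definition of evaluable for response. Either closes the gap between 10 and 15 mm.
2. **Sum of diameters.** Use the short axis for nodes in 13.2 and 13.4.1. A target node going from at least 15 mm to below 10 mm then shrinks by more than (15 − 10)/15 = 33.3%, and non-nodal targets in CR contribute a 100% fall. The sum therefore always falls by more than 30%, and the CR/SD overlap disappears.
3. **Non-target-only disease.** Add a Table 15 path for these patients and a node size rule in 13.5. This is useful even after the first edit, because patients without measurable disease are enrolled and still need a status for PFS.
4. **Target cap.** Change ten to five in the non-target definition.

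The cost is a few wording changes and matching derivation code. No visit, scan, sample or treatment rule changes.
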